8.2 ADVERSE EVENTS AND SERIOUS ADVERSE EVENTS

8.2.1 DEFINITION OF ADVERSE EVENTS

This protocol uses the definition of adverse event from the OHRP Guidance on Reviewing and Reporting Unanticipated Problems Involving Risks to Subjects or Others and Adverse Events: “Any untoward or unfavorable medical occurrence in a human subject, including any abnormal sign (for example, abnormal physical exam or laboratory finding), symptom, or disease, temporarily associated with the subject’s participation in research, whether or not considered related to the subject’s participation in the research.”

8.2.2 DEFINITION OF SERIOUS ADVERSE EVENTS

This protocol uses the FDA’s definition of serious adverse event as defined in 21CFR312.32 (b):

An adverse event is considered serious if, in the view of either the investigator or sponsor, it results in any of the following outcomes:

- Death;
- A life-threatening adverse event;
- Inpatient hospitalization or prolonging of existing hospitalization;
- A persistent or significant incapacity or substantial disruption of the ability to conduct normal life functions; or
- A congenital anomaly/birth defect.

Important medical events that may not result in death, be life-threatening, or require hospitalization may be considered serious when, based upon appropriate medical judgement, they may jeopardize the patient or subject and may require medical or surgical intervention to prevent one of the outcomes listed in this definition.

8.2.3 CLASSIFICATION OF AN ADVERSE EVENT

8.2.3.1 SEVERITY OF EVENT

For adverse events (AEs), the following guidelines will be used to describe severity.

- **Mild** – Events require minimal or no treatment and do not interfere with the participant's daily activities.
- **Moderate** – Events result in a low level of inconvenience or concerns. Moderate events may cause some interference with functioning.
- **Severe** – Events interrupt a participant's usual daily activity and may require systemic drug therapy or other treatment. Severe events are usually potentially life-threatening or incapacitating. Of note, the term "severe" does not necessarily equate to "serious".

8.2.3.2 RELATIONSHIP TO STUDY INTERVENTION/EXPERIMENTAL MANIPULATION

All adverse events (AEs) will have their relationship to study procedures, including the intervention, assessed by the study PIs based on temporal relationship and her clinical judgment. The degree of certainty about causality will be graded using the categories below.

- **Definitely Related** – There is clear evidence to suggest a causal relationship, and other possible contributing factors can be ruled out. The clinical event, including an abnormal laboratory test result, occurs in a plausible time relationship to study procedures administration and cannot be explained by concurrent disease or other drugs or chemicals. The response to withdrawal of the study procedures should be clinically plausible. The event must be pharmacologically or phenomenologically definitive.
- **Probably Related** – There is evidence to suggest a causal relationship, and the influence of other factors is unlikely. The clinical event, including an abnormal laboratory test result, occurs within a reasonable time after administration of the study procedures, is unlikely to be attributed to concurrent disease or other drugs or chemicals, and follows a clinically reasonable response on withdrawal.

- **Potentially Related** – There is some evidence to suggest a causal relationship (e.g., the event occurred within a reasonable time after administration of study procedures). However, other factors may have contributed to the event (e.g., the participant's clinical condition, other concomitant events). Although an AE may rate only as "possibly related" soon after discovery, it can be flagged as requiring more information and later be upgraded to "probably related" or "definitely related", as appropriate.
- **Unlikely to be related** – A clinical event, including an abnormal laboratory test result, whose temporal relationship to study procedures administration makes a causal relationship improbable (e.g., the event did not occur within a reasonable time after administration of the study procedures) and in which other drugs or chemicals or underlying disease provides plausible explanations (e.g., the participant's clinical condition, other concomitant treatments).
- **Not Related** – The AE is completely independent of study procedures administration, and/or evidence exists that the event is definitely related to another etiology. There must be an alternative, definitive etiology documented by the clinician.]

8.2.3.3 EXPECTEDNESS

The study PI will be responsible for determining whether an adverse event (AE) is expected or unexpected. An AE will be considered unexpected if the nature, severity, or frequency of the event is not consistent with the risk information previously described for the study procedures.

8.2.4 TIME PERIOD AND FREQUENCY FOR EVENT ASSESSMENT AND FOLLOW-UP

The occurrence of an adverse event (AE) or serious adverse event (SAE) may come to the attention of study personnel during study visits, group sessions or other interactions with a study participant, or upon review by a study monitor.

All AEs, not otherwise precluded per the protocol, will be captured on the appropriate case report form (CRF). Information to be collected includes event description, date of onset, PI's assessment of severity, relationship to study procedures (assessed only by those with the training and authority to make a diagnosis), and date of resolution/stabilization of the event. All AEs occurring while on study will be documented appropriately regardless of relationship. All AEs will be followed to adequate resolution.

Any medical or psychiatric condition that is present at the time that the participant is screened will be considered as baseline and not reported as an AE. However, if the study participant's condition deteriorates at any time during the study, it will be recorded as an AE.

Changes in the severity of an AE will be documented to allow an assessment of the duration of the event at each level of severity to be performed. Documentation of onset and duration of each episode will be maintained for AEs characterized as intermittent.

Study personnel will record events with start dates occurring any time after informed consent is obtained until the last day of study participation. At each study visit, study personnel will inquire about the occurrence of AE/SAEs since the last visit. Events will be followed for outcome information until resolution or stabilization.

8.2.5 ADVERSE EVENT REPORTING

Qualifying adverse events will be reported to the NIH funding institute.

8.2.6 SERIOUS ADVERSE EVENT REPORTING

The PIs will be responsible for conducting an evaluation of a serious adverse event. If the evaluation of the event determines that the event is related to the study, the study team shall report the results of such evaluation to the NIH and the reviewing Institutional Review Board (IRB) as soon as possible, but in no event later than 10 working days after the investigator first learns of the event.

8.3 UNANTICIPATED PROBLEMS

8.3.1 DEFINITION OF UNANTICIPATED PROBLEMS

This protocol uses the definition of Unanticipated Problems as defined by the Office for Human Research Protections (OHRP). OHRP considers unanticipated problems involving risks to participants or others to include, in general, any incident, experience, or outcome that meets all of the following criteria:

- Unexpected in terms of nature, severity, or frequency given (a) the research procedures that are described in the protocol-related documents, such as the Institutional Review Board (IRB)-approved research protocol and informed consent document; and (b) the characteristics of the participant population being studied;
- Related or possibly related to participation in the research (“possibly related” means there is a reasonable possibility that the incident, experience, or outcome may have been caused by the procedures involved in the research); and
- Suggests that the research places participants or others at a greater risk of harm (including physical, psychological, economic, or social harm) than was previously known or recognized.]

8.3.2 UNANTICIPATED PROBLEMS REPORTING

The investigator will report unanticipated problems (UPs) to the reviewing Institutional Review Board (IRB). The UP report will include the following information:

- A detailed description of the event, incident, experience, or outcome
- An explanation of the basis for determining that the event, incident, experience, or outcome represents an UP
- A description of any changes to the protocol or other corrective actions that have been taken or are proposed in response to the UP

To satisfy the requirement for prompt reporting, UPs will be reported using the following timeline:

- UPs will be reported to the IRB a within 7 calendar days of the investigator becoming aware of the event

9 STATISTICAL CONSIDERATIONS

9.1 STATISTICAL HYPOTHESES

Primary Endpoints:

For each primary outcome (MVPA, dietary risk, and veggie meter), at each of 16, 32, and 48 weeks, the statistical hypotheses are:

H0: The change in the outcome does not differ between intervention and control groups.

HA: The change in the outcome does differ between intervention and control groups.

Specifically, it is expected that AAW participating in an 8-session culturally relevant mindfulness intervention plus an exercise and nutrition education CM risk-reduction intervention will have greater sustained improvement in exercise and healthy eating behaviors at 16, 32, and 48 weeks post first intervention session, compared to AAW in an attention-control exercise and nutrition education CM risk-reduction intervention without mindfulness.

Secondary Endpoints:

For each secondary outcome (CM risk biomarker), at each of 16, 32, and 48 weeks, the statistical hypotheses are:

H0: The change in the outcome does not differ between intervention and control groups.

HA: The change in the outcome does differ between intervention and control groups.

It is hypothesized that AAW participating in an 8-session culturally relevant mindfulness intervention plus an exercise and nutrition education CM risk-reduction intervention will have greater reduction in CM risk biomarkers at 16, 32, and 48 weeks post first intervention session, compared to AAW in an attention-control exercise and nutrition education CM risk-reduction intervention without mindfulness.

Tertiary Endpoints:

Tertiary outcomes are self-reported mindfulness, stress management, positive reappraisal, self-regulation, and self-efficacy mediate effects of the intervention on exercise and nutrition.

For each tertiary outcome, at each of 16, 32, and 48 weeks, the statistical hypotheses are:

H0: The change in the outcome does not differ between intervention and control groups.

HA: The change in the outcome does differ between intervention and control groups.

9.2 SAMPLE SIZE DETERMINATION

200 participants will be enrolled (100 each in HARMONY and NEEW). Conservatively, based on prior research, comparisons of complete data on 80 participants per group are assumed, and also assume 20% attrition. Power calculations were performed with POWERLIB20 SAS/IML modules that incorporate methods to calculate power for the general linear multivariate model, which includes repeated measures data structures. Based on pilot study data, power analysis focuses on a group of representative variables addressed in the primary and secondary endpoints for CM risk factors. For primary and secondary endpoints, power is based on a separate multivariate model for these outcomes, incorporating measures from all timepoints. It is hypothesized that through improvements in self-management, women in HARMONY (experimental group) will show greater sustained improvements in exercise and healthy eating behaviors (primary endpoint) and greater reduction of CM risk biomarkers (secondary endpoint). Each hypothesis will be considered by specifying both a between-group contrast (HARMONY vs. NEEW) and the appropriate within-group contrast (three post-baseline timepoints versus baseline). This facilitates testing the null hypothesis that both groups have the same difference in population means for the change from baseline at a specific post-baseline time point against the alternative that the between-group difference of the change from baseline significantly differs from 0.

The primary endpoint at 48 weeks post first group session is tested at a significance level of 0.05; the other two timepoints will be tested using a Bonferroni correction of a two-sided 0.025 ($=0.05/2$) significance level. A compound symmetry correlation structure is assumed across all timepoints in our calculations. Based on pilot data, correlation parameters are 0.35 for BMI, 0.11 for WHR and -0.45 for A1C. With 80 participants per group (total of 160), statistical power is 85% to detect an effect size of 0.56 for BMI and exceeds 95% to detect an effect size of 0.45 for A1C and 0.59 for waist-hip ratio at each post-baseline time point.^{76,94} In tertiary endpoints, it is hypothesized that mediation of the intervention effect on the primary outcomes (exercise and healthy eating) by the tertiary outcomes (improvements in self-reported mindfulness, stress management, positive reappraisal, self-regulation, and self-efficacy). [In simulations of power for mediation tests, Fritz and Mackinnon⁹⁵ found that when effect sizes (standardized regression coefficients) relating the intervention to the mediator and the mediator to the outcome are all ≥ 0.26 (small- medium, according to Cohen's [1988] definition)⁹⁶, the sample size ($n=160$)

is adequate for at least 80% power. If either effect size is much smaller (simulations used 0.14), the study will be underpowered.

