Waist circumference will be measured at the midpoint between the upper iliac crest and lower costal margin in the midaxillary line. Study personnel will record two waist circumference measurements. The mean of these measurements will be used for the waist-to-hip ratio.

Waist circumference will be measured at baseline and 16, 32, and 48 weeks post first group session.

IL-6 and CRP

Specimens for the measurement of IL-6 and CRP will be collected using standard venipuncture.

The phlebotomy procedure to obtain the IL-6 and CRP measurements will be completed at baseline and 16, 32, and 48 weeks post first group session.

HgbA1C

HgbA1C will be assessed using a fingerstick procedure at baseline and 16, 32, and 48 weeks post first group session.

Blood Pressure

Blood pressure will be collected by an electronic sphygmomanometer after a five-minute rest in the sitting position. Study personnel will record three blood pressure measurements, and the average value will be used for analysis.

Blood pressure will be measured at baseline and 16, 32, and 48 weeks post first group session.

Contextualized Stress Scale

The participant's racial and gendered stress exposure will be measured using the Contextualized Stress Measure, which includes 69 items on a 5-point scale. The Contextualized Stress Measure is divided into six subscales, including race/racism, burden, personal history, workplace, coping and support, and stress states. Score ranges from 0 to 345, with higher scores associated with increased stress exposure.

This questionnaire will be performed at baseline and 16, 32, and 48 weeks post first group session. The data will be entered electronically by the patient through REDCap survey; however, paper copies of the questionnaire may be used if necessary.

Network Stress Scale

The participant's indirect and self-stress will be measured using the Network Stress Scale, which includes 10 items on a 4-point scale. The Network Stress scale assesses both exposure and appraisal of events that happened to both self and close family members and friends. Higher scores represent higher exposure and appraisal. Score ranges from 0, with 10 scores associated with a higher amount of indirect and self-stress.

This questionnaire will be performed during the pre-baseline period and 16, 32, and 48 weeks post first group session. The data will be entered electronically by the patient through REDCap survey; however, paper copies of the questionnaire may be used if necessary.

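### Section 9.2 prints an A1C correlation of -0.45 under compound symmetry over four timepoints; no such covariance exists, so the stated A1C power above 95% is unsupported.

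*Combined protocol and SAP*

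**What the plan says.** Section 9.2 describes a general linear multivariate power model "incorporating measures from all timepoints". Its within-group contrast is "the appropriate within-group contrast (three post-baseline timepoints versus baseline". On the covariance it says: "A compound symmetry correlation structure is assumed across all timepoints in our calculations". The parameters follow: "Based on pilot data, correlation parameters are 0.35 for BMI, 0.11 for WHR and -0.45 for A1C".

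For A1C and waist-hip ratio, 9.2 reports that power "exceeds 95% to detect an effect size of 0.45 for A1C and 0.59 for waist-hip ratio at each post-baseline time point". For BMI it reports: "With 80 participants per group (total of 160), statistical power is 85% to detect an effect size of 0.56 for BMI". It does not say what the correlations are correlations of, or in which SD the effect sizes are expressed.

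Section 8.1 fixes the number of A1C measures: "HgbA1C will be assessed using a fingerstick procedure at baseline and 16, 32, and 48 weeks post first group session". Section 3 lists change in glycosylated hemoglobin to 48 weeks as secondary outcome 2.8. Section 9.4.1 uses alpha 0.05, except for the 16- and 32-week tests of primary and secondary outcomes, which use 0.025.

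**The concern.** Read together, these passages give A1C a 4 x 4 correlation matrix with -0.45 in every off-diagonal cell. Four variables cannot all be negatively correlated with one another to that degree. The A1C entry therefore rests on a covariance that no data set can have.

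Section 9.2 gives numerical outcome power for only three representative variables, and A1C is one of them. All three correlations are attributed to the pilot data. An inadmissible value raises the question of what was extracted for A1C, and whether the BMI and waist-hip values are the same kind of quantity.

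**Working it through.** **Inputs.** From 9.2: compound symmetry; correlation ρ = -0.45 for A1C, 0.35 for BMI and 0.11 for waist-hip ratio; effect size 0.45 for A1C; 80 per group. From 8.1: four A1C measures. From 9.2 and 9.4.1: alpha 0.05 at week 48 and two-sided 0.025 at weeks 16 and 32. I take 0.05 as two-sided too.

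**Step 1: is the matrix possible?** A compound-symmetric correlation matrix for p measures has eigenvalue 1 - ρ (p - 1 times) and eigenvalue 1 + (p - 1)ρ (once). It is valid only if ρ ≥ -1/(p - 1).

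| Measures p | Lower bound for ρ | 1 + (p - 1)(-0.45) | Admissible? |
|---|---|---|---|
| 2 | -1 | 0.55 | yes |
| 3 | -0.5 | 0.10 | yes |
| 4 | -0.333 | -0.35 | no |

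Equivalently, the sum of a woman's four A1C values would have variance 4 + 12(-0.45) = -1.4 in units of σ². For BMI and waist-hip ratio the smallest eigenvalues at p = 4 are 0.65 and 0.89, so those two inputs are admissible.

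**Step 2: does the stated figure reproduce at the printed value?** A single baseline-to-visit change involves only two measures, so power can be calculated at -0.45. I used a two-sample t test with 158 degrees of freedom and noncentrality d√(80/2), where d is the effect divided by the relevant SD.

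- Effect in raw SD units, change score: SD = √(2(1 + 0.45)) = √2.9 = 1.703; d = 0.45/1.703 = 0.264; power 38% at alpha 0.05 and 28% at 0.025.
- Effect in change-score SD units: d = 0.45; power 81% / 72%.
- Baseline-adjusted (ANCOVA), effect in raw SD units: SD = √(1 - 0.45²) = 0.893; d = 0.504; power 89% / 82%.

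None of these exceeds 95%. For comparison, the raw-SD change-score form gives about 87% / 80% for BMI, either side of the stated 85%. For waist-hip ratio it gives 79% / 70%, against 96% / 93% in change-score SD units. No single one of these scales clearly underlies all three stated figures.

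**Step 3: what would an admissible value give?** The documents supply no other A1C correlation, so this is a range under assumption: effect 0.45 in raw SD units, 80 per arm, d = 0.45/√(2(1 - ρ)).

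| ρ | SD of change | d | Power, alpha 0.05 | Power, alpha 0.025 |
|---|---|---|---|---|
| -1/3 | 1.633 | 0.276 | 41.0% | 30.4% |
| 0 | 1.414 | 0.318 | 51.6% | 40.3% |
| +0.45 | 1.049 | 0.429 | 77.0% | 67.4% |
| 0.6 | 0.894 | 0.503 | 88.5% | 82.0% |
| 0.7 | 0.775 | 0.581 | 95.5% | 92.0% |
| 0.8 | 0.632 | 0.712 | 99.4% | 98.7% |

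If 0.45 is in change-score SD units, ρ cancels and power stays at about 81% / 72% throughout.

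**The case against.** The best defence is that the printed power refers to each post-baseline timepoint. Each such comparison uses one change from baseline, and that 2 x 2 block is valid at -0.45. Even the three change scores jointly have a valid covariance there (eigenvalues 1.45, 1.45 and 5.8 in units of σ²). This is correct, and it means that the contrasts alone do not expose the problem. It does not make the four-measure structure in 9.2 possible. Nor does it recover the stated figure, as step 2 shows; a joint 3-df test of the three changes gives only 37% / 26% in raw SD units.

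A second defence is that -0.45 describes three quantities, such as the follow-ups alone or the change scores, for which the bound is -0.5. The documents cannot exclude this, but 9.2 would then misdescribe its own calculation. The change-score version also conflicts with compound symmetry of the raw measures. Under that structure, two changes from the same baseline have covariance 1 - ρ and variance 2(1 - ρ) each, so their correlation is always +0.5.

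A reader might infer that the value is simply a sign error. The documents do not say so, and +0.45 still gives only 77% / 67% in raw SD units.

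A reader might also infer that the random intercept in 9.4.1 independently rules out a negative correlation. It does not: 9.4.1 adds a within-subject covariance matrix chosen by AIC among unstructured, compound symmetric and autoregressive forms, and this permits negative marginal correlation.

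**Conclusion.** The point holds for the A1C entry in 9.2. As printed, the correlation lies below the admissible bound (-0.45 against -0.333), and the power of more than 95% does not follow from the stated inputs on any of the scales tried. The impossibility is algebraic and depends only on there being four measures, which 9.2 and 8.1 together support. The size of the power shortfall depends on the undefined effect-size scale. It ranges from large (41% / 30% at ρ = -1/3, raw SD units) to moderate (about 81% / 72%, change-score SD units).

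The stated figure is unsupported, not refuted: in raw SD units a correlation somewhat above 0.7 would give more than 95% at both alpha levels. The documents also do not show which matrix was actually entered.

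A reader might go further and conclude that the sample size of 200 falls. That is not supported. A1C is a secondary endpoint, 9.2 presents it as one of several representative variables and does not say that N was solved from it, the lowest power stated for the three variables is the 85% for BMI, and the BMI and waist-hip correlations are admissible.

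**What to change.** In 9.2:

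1. Recheck the A1C correlation against the pilot data, including its sign.
2. State what was correlated (raw values, follow-ups only, changes, or baseline with change) and over how many visits. Confirm that 0.35 and 0.11 are the same kind of quantity.
3. State whether effect sizes are in raw or change-score SD units.
4. Rerun the A1C power with an admissible common correlation or the estimated 4 x 4 matrix, at alpha 0.05 for week 48 and 0.025 for weeks 16 and 32.
5. Restate the A1C power, or delete it if the pilot data cannot supply a usable value.

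The cost is about an hour of statistician time and a sentence or two in 9.2. The restated power may be less favourable. Neither N nor the planned analysis changes.
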